4.2.2 Safety in Hemodialysis Patients

A review of the aggregate safety data shows that CR845 was well tolerated in hemodialysis patients when administered after each dialysis session for up to 8 weeks at IV doses ranging from 0.5 mcg/kg to 6 mcg/kg. Although patients exposed to CR845 reported more adverse events compared with placebo patients, most events were mild or moderate in nature. Generally mild, transient paresthesias (facial tingling) and/or hypoesthesias (in different anatomic locations), mostly on the first week of dosing, as well as headache, dizziness, and somnolence, were the most frequently reported adverse events associated with CR845 administration. Of note, side effects (eg, dysphoria and hallucinations) commonly associated with centrally-acting kappa opioids were not reported in patients exposed to CR845. Consistent with its lack of affinity for mu-opioid receptors, CR845 did not cause euphoria, respiratory depression, or reduction in oxygen saturation.

CR845-CLIN2101 (Part A) evaluated the safety, pharmacokinetics, and efficacy of repeated IV doses of CR845 compared to placebo over an 8-week treatment period in 174 hemodialysis patients. This study is the longest treatment period evaluated to date in hemodialysis patients and no clinically important or significant safety findings related to CR845 were noted. As expected with patients on hemodialysis, a significant number of the reported serious adverse events (SAEs) were considered not treatment-related, but related to the disease and/or comorbid conditions. There were 31 (17.8%) of 174 patients randomized and treated in the study who had treatment-emergent SAEs. Of the 31 SAE reports, 4 (9%) occurred in 45 placebo-treated patients and 27 (21%) in 129 CR845-treated patients. Only 1 SAE of mental status changes (moderate in severity) in a patient who received CR845 1.5 mcg/kg IV was considered by the Investigator to be probably related to study drug. However, based on the Sponsor's medical review, an alternate etiology of urgent/emergent hypertension offers a more plausible explanation for the acute change in mental status. There were 4 patient deaths (2.3%) in the study, all of which were considered not related to the study drug.

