 - h. Training on Worst Itching Intensity NRS will be conducted on the first day of the Run-in Period (Day -7).
 - i. Training on ShOWS on Day -7 and first day of Week 13.
 - j. Training on Skindex-10 Scale and 5-D Itch Scale may be performed at any time during the week prior to randomization or on Day 1 of the Double-blind Treatment Period
 - k. Patients will be requested to complete their Worst Itching Intensity NRS worksheets each day at a similar time (either at home on non-dialysis days around the normal start time of their dialysis or in the dialysis unit). On dialysis days, the worksheets will be completed prior to or during dialysis, but must be completed prior to dosing.
 - l. During the Discontinuation Period, Worst Itching Intensity NRS worksheets will be completed on dialysis days only.
 - m. 5-D Itch Scale and Skindex-10 Scale completed on Day 1 and the first visit of Weeks 5, 9 and 11 (on Days 29, 57 and 71) and Week 13 (Day 85). 5-D Itch scale will preferably be completed first. If the first visit of the week is missed, the patient may complete the worksheets at their next visit for the same week. The worksheets will be completed prior to or during dialysis (preferably within 1 hour of the dialysis), but must be completed prior to dosing.
 - n. ShOWS worksheets will be completed daily through the entire Discontinuation Period starting on Day 85. The OOWS worksheets will be completed at each dialysis visit during the Discontinuation Period starting on Day 85. On the day of a dialysis visit, the OOWS and the ShOWS will be completed during the first **hour** (+1-hour window allowed) of dialysis so that dialysis-associated patient fatigue and other potential side effects related to the dialysis procedure should minimally interfere with the completion of the scales.
 - o. Biomarker samples must be collected prior to the start of dialysis on Day 1 and Day 85.
 - p. Concomitant medications including antipruritic medication will be updated at each dialysis visit during the Double-blind Treatment Period, and until the end of the Discontinuation Period.
 - q. Sites have the option to conduct the Screening Visit during the Run-in Period at the discretion of the Investigator

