6.5.3.2 Skindex-10 Scale

Developed specifically for uremic pruritus, the Skindex-10 Scale (Appendix 3, Section 14.3) is an instrument for measurement of quality-of-life that correlates with itch intensity [Mathur 2010]. Patients are asked to mark 1 of 7 boxes numbered from 0 (labeled with the anchor phrase “never bothered”) to 6 (labeled as “always bothered”) for each of the 10 questions describing how often they have been bothered by their itch and its impact over the past week. The total score is the sum of the numeric value of each answered question. The total score is subdivided into 3 domain scores, which are sums of the scores of the following questions: disease domain (questions 1 to 3), mood/emotional distress domain (questions 4 to 6), and social functioning domain (questions 7 to 10).

6.5.3.3 5-D Itch Scale

The 5-D Itch Scale was developed as a brief, multidimensional questionnaire designed to be useful as an outcome measure in clinical studies. The 5 dimensions of itch assessed are degree, duration, direction, disability, and distribution (Appendix 4, Section 14.4).

Patients are asked to mark boxes that best describe the impact of their itch over the past 2 weeks. The scale has been validated in patients with chronic pruritus, including hemodialysis patients and has been shown to be sensitive to changes in pruritus over time [Elman 2010].

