8.2.2 Primary Efficacy Analysis

In the primary efficacy analysis, missing NRS data at the end of Week 12 will be imputed using a multiple imputation (MI) approach, assuming that subjects who discontinue double-blind treatment early would have similar Worst Itching Intensity NRS scores as other subjects in their respective treatment arm who have complete data:

- Intermittent missing NRS scores will first be imputed using the Markov Chain Monte Carlo (MCMC) method implemented with the SAS MI procedure, which is appropriate for non-monotonic missing data.
- The monotone missing NRS values will then be multiply imputed with the SAS MI procedure using the monotone regression method.

- For each stage, MI will be performed within treatment group with covariates for baseline NRS score, both randomization stratification factors, and the non-missing NRS scores for each week. Should convergence issues occur due to small cell size for the categorical covariates at either stage, those covariates will be removed from the model.
- The proportion of subjects who have an improvement from baseline with respect to the weekly mean of the daily 24-hour Worst Itching Intensity NRS score ≥ 3 points will be calculated for each imputed dataset. Differences between CR845 0.5 mcg/kg and placebo with respect to the primary endpoint will be compared using a logistic regression model containing terms for treatment group, baseline NRS score, use of anti-itch medication during the week prior to randomization, and presence of specific medical conditions.
- Twenty imputations will be performed.
- Results of the logistic regression on the multiply imputed data sets will be summarized by the SAS MIANALYZE procedure.

The observed number and proportion of subjects with ≥ 3 -point improvement among the non-imputed data will be reported along with the imputed data logistic regression model-based estimates of the proportions of responders, odds ratio, 95% confidence intervals (CIs), and p-value.

Sample size adjustment

The above MI process will be implemented completely independently among subjects contributing the interim results and those following the interim analysis. Likewise, the logistic regression and results described above will be generated independently for both samples, with the samples combined and adjusted as follows:

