8.2.4.3 Key Secondary Analyses

5-D Itch Scale and the Skindex-10 Scale

The 5-D Itch Scale and the Skindex-10 Scale scores will be analyzed only at Week 12 using an analysis of covariance (ANCOVA). The model will contain treatment as fixed effects, with baseline score and the randomization stratification variables as covariates. The baseline 5-D total score and the Skindex-10 total score will be defined as the value collected on Day 1, prior to randomization. This is a change from the final protocol dated 21DEC2017 and is being implemented to address the FDA advice received on 10JAN2019 stating that “*the analysis [of continuous efficacy endpoints] should be based on only data from one timepoint (e.g. Week 12); however, modeling approaches using all timepoints may be used as supportive analyses.*”

Additionally, subjects who discontinue treatment but continue on study and have 5-D and Skindex-10 scores recorded will have these scores censored following discontinuation of treatment; missing data rules will apply to these censored values as though they had missing values/ dropped out from the study entirely.

For each domain in each questionnaire, missing values at Week 12 will be imputed using an MI approach, assuming that subjects who discontinue double-blind treatment early would have similar 5-D Itch and Skindex-10 scores as other subjects in their respective treatment arm that have complete data. All available visits will be included in the MI to

better inform the Week 12 imputed results. The MI approach will proceed as follows, using all ITT subjects (that is, it will not be split into IA subjects and post- IA subjects):

- Intermittent missing scores will first be imputed using the Markov Chain Monte Carlo (MCMC) method implemented with the SAS MI procedure, which is appropriate for non-monotonic missing data.
- The monotone missing values will then be multiply imputed with the SAS MI procedure using the monotone regression method.
- For each stage, MI will be performed within treatment group with covariates for baseline score, both randomization stratification factors, and all non-missing visit scores for each domain of the questionnaire. Should convergence issues occur due to small cell size for the categorical covariates at either stage, they will be removed from the model.
- Twenty imputations will be performed for each domain.

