- m. 5-D Itch Scale and Skindex-10 Scale completed on the first visit of Weeks 5, 9 and 11 (on Days 29, 57 and 71). 5-D Itch scale will preferably be completed first. If the first visit of the week is missed, the patient may complete the worksheets at their next visit for the same week.
- n. ShOWS worksheets will be completed daily through the entire Discontinuation Period starting on Day 85. The OOWS worksheets will be completed at each dialysis visit during the Discontinuation Period starting on Day 85. On the day of a dialysis visit, the OOWS and the ShOWS will be completed during the first 30 minutes (+1-hour window allowed) of dialysis so that dialysis-associated patient fatigue and other potential side effects related to the dialysis procedure should minimally interfere with the completion of the scales.
- o. Biomarker samples must be collected prior to the start of dialysis.
- p. Concomitant medications including antipruritic medication will be updated at each dialysis visit during the Double-blind Treatment Period, and until the end of the Discontinuation Period.
- q. Concomitant medications will be updated at each dialysis visit until the Discontinuation Period. Antipruritic medication will be recorded at each dialysis visit during the Run-in Period.
- r. Sites have the option to conduct the Screening Visit during the Run-in Period at the discretion of the Investigator
 - s. Preferably to be completed on Wednesday/Thursday each week during the Run-in Period, the Double-blind Treatment Period and the Discontinuation

Period. Not to be completed on Monday/Tuesday. A set of prespecified events will be verified with the patient by the site staff.

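### The 5-D Itch and Skindex-10 imputation leaves out the weekly NRS, so early stoppers are imputed from baseline information only; this can bias the treatment difference in either direction and is cheap to repair

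*SAP*

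**What the plan says.** For the two questionnaires, SAP 8.2.4.3 makes an ANCOVA at Week 12 on multiply imputed data the main analysis. Imputation is within arm, with "covariates for baseline score, both randomization stratification factors, and all non-missing visit scores for each domain of the questionnaire". The section also says that all available visits enter the imputation, which in context means questionnaire visits. Its stated assumption is that early stoppers "would have similar 5-D Itch and Skindex-10 scores as other subjects in their respective treatment arm that have complete data". Subjects who stop treatment but stay on study "will have these scores censored following discontinuation of treatment".

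The primary endpoint is handled differently. SAP 8.2.2 lists "covariates for baseline NRS score, both randomization stratification factors, and the non-missing NRS scores for each week", and the sample code in SAP section 14 carries baseline and all 12 weekly NRS values.

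The timing matters. Protocol Table 2, footnote m, has the "5-D Itch Scale and Skindex-10 Scale completed on Day 1 and the first visit of Weeks 5, 9 and 11", then on Day 85. The NRS is recorded daily; a weekly mean needs at least 4 daily scores (SAP 8.1.1), and NRS scores after treatment discontinuation are censored (SAP 8.2.1). The Early Termination Visit is the first dialysis after the last dose (Protocol 6.3.1). It is assigned to a planned visit only if it falls within 3 days of it (SAP 3.1).

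**The concern.** Between Day 1 and Day 29 the questionnaires record nothing, while the NRS is recorded every day. A subject who stops in that gap may have a recorded course of itch, yet the imputation for the two quality-of-life endpoints does not look at it. Protocol 6.5.3.2 says that the Skindex-10 "is an instrument for measurement of quality-of-life that correlates with itch intensity", so the omitted data should be informative at least for that scale. If poor early responders stop more often in one arm, their recorded poor course is replaced by draws typical of the subjects who stayed.

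The 5-D is the first gated secondary endpoint (SAP 8.1.3) and opens the tests of Skindex-10 and then of the ≥4-point response. No other planned analysis would reveal the problem. The supportive MMRM also omits the NRS, and a subject with no post-baseline score contributes nothing to it. The nonresponder, MNAR and tipping-point analyses in SAP 8.2.3 are for the primary endpoint only. The Per Protocol rules on doses and NRS weeks are applied while the subject is in the study, so stopping early does not by itself exclude anyone.

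**Working it through.** The plan gives no power, SD, dropout or correlation figure for either questionnaire, so there is no plan figure to reproduce here. (The primary endpoint's stated 96% power recomputes as 96.3%, but has no bearing on this point.)

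**Step 1: who has only baseline information.** Day 29 ± 3 gives a mapping window of Days 26 to 32. NRS weeks are Days 2–8, 9–15, 16–22 and 23–29.

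| Last dose (Day) | Early Termination (Day) | Mapped to Day 29? | Weekly NRS means that can exist |
|---|---|---|---|
| 1 | 3 | no | none (at most Days 2–3) |
| 5 | 8 | no | Week 1 |
| 12 | 15 | no | Weeks 1–2 |
| 19 | 22 | no | Weeks 1–3 |
| 22 | 24 | no | Weeks 1–3 |
| 24 | 26 | yes, unless censored | at least Weeks 1–3 |
| 26 | 29 | yes, unless censored | Weeks 1–4 |

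Up to a last dose on Day 22, only baseline score and strata inform Week 12. For Days 24 and 26 the answer depends on whether the censoring rule removes the Early Termination score, which the SAP does not settle. Later stoppers lose information too. With a last dose on Day 50, Early Termination is on Day 52, outside Day 57 ± 3. NRS Weeks 5, 6 and 7 (Days 30–36, 37–43, 44–50) then go unused.

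**Step 2: size of the bias.** All inputs are assumptions. Let p be the fraction of an arm stopping before the first repeat questionnaire, ρ the correlation of the tendency to stop with poor early NRS, and r the correlation of early NRS with the Week 12 score given baseline. In residual SD units, imputing from baseline alone makes an arm look better by p × (stopper–completer gap) = r·ρ·φ(z_p)/(1 − p), where φ(z_p) is the normal density at the upper p quantile. The bias in the difference is the CR845 term minus the placebo term.

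- p = 10%, r = 0.5, ρ = 0.7: 0.35 × 0.1755/0.90 = 0.068
- p = 5%, same r and ρ: 0.35 × 0.1031/0.95 = 0.038
- ρ = 0 or r = 0: zero

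A simulation used 175 per arm, 20 within-arm regression imputations, ANCOVA and Rubin's rules. The true effect was 0.39 SD, the smallest Phase 2 NRS effect size in Protocol 4.2.3, borrowed only as an illustration. Positive bias favours CR845. Percentages divide by the complete-data estimate (0.383 to 0.393). The last column is one-sided rejection in favour of CR845 at zero true effect.

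| Early stopping, CR845 vs placebo | ρ, CR845 / placebo | r | Formula | Simulated bias | % of effect | Rejection |
|---|---|---|---|---|---|---|
| 5 vs 5% or 10 vs 10% | 0.7 / 0.7 | 0.5 | 0 | 0.001 | 0 | 2.5–2.6% |
| 10 vs 5% | 0.7 / 0.7 | 0.5 | 0.030 | 0.032 | 8 | 4.3% |
| 5 vs 2% | 0.7 / 0 | 0.5 | 0.038 | 0.038 | 10 | 6.4% |
| 10 vs 5% | 0.7 / 0 | 0.3 | 0.041 | 0.043 | 11 | 4.8% |
| 10 vs 5% | 0.7 / 0 | 0.5 | 0.068 | 0.071 | 19 | 8.4% |
| 10 vs 3% | 0.7 / 0 | 0.7 | 0.096 | 0.097 | 25 | 13.4% |
| 5 vs 10% | 0.7 / 0.7 | 0.5 | −0.030 | −0.030 | −8 | 1.1% |
| 10 vs 10% | 0 / 0.7 | 0.5 | −0.068 | −0.068 | −18 | 0.4% |

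With early NRS in the imputation model, bias was within 0.001 SD throughout and rejection was 2.2% to 3.5%. With complete data, rejection was 2.1% to 3.3%.

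A second simulation worked on the 5-D scale: 200,000 per arm, assumed NRS/5-D correlation 0.75 at Week 12, and more early stopping on CR845 (10–13% vs 3–4%), related to poor response. It gave −1.39 against a truth of −1.32 (0.07/1.32 = 5%) and −1.47 against −1.34 (0.13/1.34 = 10%). With NRS added the results were −1.33 and −1.34. With 16–19% vs 4–5% stopping, the overstatement was 8% to 17%.

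**The case against.** The strongest reply is that the SAP states its missing-at-random assumption, uses every questionnaire visit and adds a supportive MMRM, so the choice of auxiliary variables is a refinement. The sizes also rest on invented inputs. Both simulations make stopping depend on NRS, so adding NRS must remove the bias. Both impute one score, whereas the SAP imputes domains and then sums them. In the first, every stopper has an early NRS value. The shifts are small next to sampling error. Assuming a 5-D SD of 3 to 5 and 175 per arm, the standard error is SD × √(2/175) = 0.32 to 0.53, so 0.07 to 0.13 points is about 0.13 to 0.4 standard errors. All of this stands as a limit on the size. It does not explain why recorded on-treatment itch is used for one endpoint and ignored for the next.

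A reader might infer more than the documents support:

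- **That the bias favours CR845.** The direction depends on the stopping pattern. More adverse events on CR845 in earlier studies (Protocol 4.2.2) make unequal stopping plausible, but no passage links stopping to poor itch relief.
- **That early stopping is likeliest in the first week.** The words "mostly on the first week of dosing" in Protocol 4.2.2 describe generally mild, transient paresthesias and hypoesthesias, not stopping.
- **That Weeks 1–3 NRS means exist for every early stopper.** A subject who stops in the first days may have only baseline NRS, and the fix helps least there.
- **That the ≥4-point estimate is biased too.** It uses the primary NRS imputation (SAP 8.2.4.3), so only the gate to its test is affected.
- **That early stoppers are assigned the arm average.** They receive random draws around a mean conditional on baseline score and strata.

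**Conclusion.** The omission is real, and nothing else in either document closes it. Its effect is conditional: about zero with equal stopping patterns or stopping unrelated to itch, an overstatement when response-related early stopping is more frequent or more selective on CR845, and an understatement in the reverse case. Under the assumed unfavourable patterns the overstatement is about 5% to 25% of the difference. The top of that range needs r = 0.7 and response-related stopping on CR845 only. The rejection rates are for the 5-D test taken alone; in the trial it is inferential only after the primary endpoint succeeds. The point supports a cheap improvement to the SAP. It does not show that the planned result will be wrong.

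**What to change.** In the third imputation bullet of SAP 8.2.4.3, add baseline NRS and the weekly mean NRS scores, censored at treatment discontinuation as in SAP 8.2.1, as auxiliary variables in both PROC MI steps. List them in time order with the questionnaires: NRS Weeks 1–4 before Day 29, Weeks 5–8 before Day 57, Weeks 9–10 before Day 71, and Weeks 11–12 before Day 85. State that NRS values imputed here serve only as auxiliaries and do not replace those of the primary analysis. The ANCOVA, the gate and the assumption of similarity within arm stay as they are. One sentence should also settle whether an Early Termination score on Day 26 or 29 survives the censoring rule.

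The cost is SAP wording, a larger imputation model within arm and a second set of imputed NRS values. The primary imputation already carries 13 NRS variables per arm on about half the subjects, because it is split at the interim and this one is not. If the larger model does not converge, use a prespecified reduced set of NRS weeks. The change does not help where stopping is unrelated to recorded itch but later worsening goes unobserved; that would need an MNAR or tipping-point analysis, which the SAP does not plan for these endpoints.

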- For each questionnaire, the total score at each visit will be computed from the domain scores for each imputed dataset.
- The ANCOVA analysis described above will be implemented for each imputed dataset.
- Results of the ANCOVA on the multiply imputed data sets will be summarized by the SAS MIANALYZE procedure.

Since the observed change from baseline at Week 12 among the non-imputed data will be reported with the MMRM analyses described below, only the LS means, standard errors, 95% CIs, and differences between treatment groups reported with LS means, standard errors, and 95% CIs from the ANCOVA on the imputed data will be reported. The analysis will be completed for both the ITT and PP Populations.

Additionally, the 5-D Itch Scale and the Skindex-10 Scale scores will be analyzed using a mixed effects model with repeated measures (MMRM). The model will contain treatment, week, and treatment-by-week interaction as fixed effects, and baseline score and the randomization stratification variables as covariates. The baseline 5-D total score and the Skindex-10 total score will be defined as the value collected on Day 1, prior to randomization. Repeated measures will include values assigned at the end of Weeks 4, 8, 10, and 12 (end of treatment); see Section [3.1](#) for visit windowing.

It is important to note that, in HD subjects, the study drug administered during the last dialysis of a particular week is not cleared until the first dialysis of the next week. Therefore, measurements that would reflect treatment effect at the end of a specific week (e.g., Week 4) and labelled “end of Week xx” will actually be collected during the first day of the next week (e.g., Week 5).

An unstructured covariance matrix will be used to model the within-subject errors. Should the model fail to converge, a compound symmetric covariance matrix will be used instead. The Kenward-Roger approximation will be used to estimate the denominator degrees of freedom. Missing scores will not be imputed. Assuming that the data are

MAR, the estimates of the treatment differences calculated from the MMRM described above are unbiased.

Standard descriptive statistics will be reported for each time point on the values and changes from baseline along with the least squares (LS) means, standard errors, 95% CIs and differences between treatment groups reported with LS means, standard errors, and 95% CIs.

Worst Itching Intensity ≥ 4 -Point Improvement

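### As most naturally read, SAP 8.2.4.3 imputes each 5-D Itch and Skindex-10 domain in its own run and then sums them; unless the domains are drawn jointly, the standard errors of the first two gated secondary tests are too small

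*SAP*

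**What the plan says.** SAP 8.2.4.3 makes a Week 12 ANCOVA on the total score the main analysis of both questionnaires, with multiple imputation of the domains: "For each domain in each questionnaire, missing values at Week 12 will be imputed using an MI approach". Intermittent gaps are filled by MCMC first. Then: "The monotone missing values will then be multiply imputed with the SAS MI procedure using the monotone regression method".

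Both steps are done within treatment group. The covariates are the baseline score, both stratification factors and "all non-missing visit scores for each domain of the questionnaire". The next two bullets read "Twenty imputations will be performed for each domain" and "For each questionnaire, the total score at each visit will be computed from the domain scores for each imputed dataset". The ANCOVA is run on each completed dataset and pooled with MIANALYZE.

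Other facts that bear on the point:

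- The 5-D Itch has five domains (SAP 8.2.4.1) and the Skindex-10 has three (SAP 8.2.4.2).
- Patients who stop treatment but stay on study "will have these scores censored following discontinuation of treatment".
- SAP 8.1.3 tests the 5-D total first and the Skindex-10 total second, each by this ANCOVA at two-sided 5%. The ≥4-point NRS endpoint follows.
- The sample code in SAP section 14 covers only the NRS.
- An MMRM on total scores without imputation is kept, and SAP section 12 labels it a sensitivity analysis.

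**The concern.** The SAP does not say whether the domains of a questionnaire are drawn together or one at a time. A single joint run gives one set of 20 datasets, so tying the number 20 to each domain adds something only if each domain has its own run.

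Domains of one questionnaire share within-patient variation at a given visit. When a patient has stopped treatment, all Week 12 domains are missing together, and separate runs give each an independent residual. Their sum then varies too little, both within a completed dataset and between datasets, so both parts of Rubin's variance fall short.

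The affected analysis is the confirmatory one. If the pooled SE is too small, the 5-D and Skindex-10 tests exceed their 5% level, their confidence intervals are too narrow, and the gate to the ≥4-point endpoint opens too easily.

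**Working it through.** **Plan's own figure.** The documents give no SD, SE or power for either questionnaire, so only the arm size can be checked. With 175 per arm and a continuity-corrected two-sided 5% test, power for 30% against 50%, 48%, 46% and 45% comes to 96.3%, 92.0%, 84.8% and 79.9%. The plan states 96%, 92%, 84% and 79%. The 90%-power sample sizes (134, 164, 204, 230, 262 per arm) reproduce exactly.

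**Mechanism.** Let D domains have equal Week 12 residual variance s² and residual correlation r.

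- Drawn jointly, the residual variance of the imputed total is D·s²·[1 + (D − 1)r].
- Drawn independently, it is D·s².
- The ratio is 1/[1 + (D − 1)r]. For illustration, r = 0.6 gives 1/3.4 = 0.29 for five domains and 1/2.2 = 0.45 for three.
- Rubin's total variance is W + (1 + 1/20)B. Both W and B are computed from these totals.

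**Simulation inputs from the SAP.** 175 per arm; five or three domains; baseline plus four visits ("Repeated measures will include values assigned at the end of Weeks 4, 8, 10, and 12"); monotone regression within arm; 20 imputations; ANCOVA on the total adjusted for baseline.

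**Inputs assumed.** 5% to 25% missing at Week 12, at random; between-domain correlation 0.6 or 0.3; within-domain correlation over time 0.6; normal scores of equal variance; no true effect.

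**Results, 2000 trials per row.** Separate means that each domain is imputed from its own history. Ratio is mean reported SE over the true SD of the estimate.

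| Domains | Corr. | Missing | SE separate | SE joint | Ratio separate | Type I separate | Ratio joint | Type I joint |
|---|---|---|---|---|---|---|---|---|
| 5 | 0.6 | 5% | 0.3507 | 0.3653 | 0.975 | 5.8% | 1.012 | 5.0% |
| 5 | 0.6 | 10% | 0.3480 | 0.3780 | 0.929 | 6.8% | 1.000 | 5.5% |
| 5 | 0.6 | 15% | 0.3455 | 0.3913 | 0.892 | 7.8% | 1.005 | 4.8% |
| 5 | 0.6 | 25% | 0.3429 | 0.4247 | 0.849 | 10.3% | 1.034 | 4.3% |
| 5 | 0.3 | 15% | 0.2849 | 0.3153 | 0.943 | 6.5% | 1.034 | 4.3% |
| 3 | 0.6 | 10% | 0.2204 | 0.2336 | 0.943 | 6.4% | 0.998 | 5.0% |
| 3 | 0.6 | 15% | 0.2206 | 0.2407 | 0.939 | 7.1% | 1.019 | 4.5% |
| 3 | 0.6 | 25% | 0.2236 | 0.2588 | 0.894 | 8.2% | 1.026 | 4.4% |

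Monte Carlo error is about 0.5 points on type I error and 1.6% on the ratios.

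- **Reported SE, separate against joint, at 15% missing and correlation 0.6:** 1 − 0.3455/0.3913 = 12% lower for five domains; 1 − 0.2206/0.2407 = 8% lower for three.
- **True spread:** it hardly differs between the two methods (0.3874 and 0.3892 for five domains at 15%). The reported SE is what goes wrong.
- **Consistency check:** a ratio of 0.892 implies a normal-theory level of 2[1 − Φ(1.96 × 0.892)] = 8.0%, against 7.8% simulated.

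**Other domains as predictors, still one run per domain.** At 15% missing and correlation 0.6 (300 trials), the ratio is 0.938 for three domains and 0.873 for five. With own history only, the same runs give 0.936 and 0.867. Past scores of the other domains do not recover the shared Week 12 residual.

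**The case against.** The strongest reply is that the text also allows a joint model. Taken literally, the covariate bullet puts every domain's visit scores into the imputation model. A single joint call with 20 imputations also gives every domain 20 imputations, and forming totals within each imputed dataset fits one dataset holding all domains. The matching bullet for the primary analysis (SAP 8.2.2) has no per-domain wording, but the NRS is a single score, so that contrast is not decisive. Under a joint draw there is no shortfall. This stands: a reader might infer that the plan definitely discards the between-domain correlation, and the documents do not establish that.

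It does not settle the matter. The same bullet can be met by one run per domain with the other domains as predictors, and that version fails almost as badly. Only a joint draw works, and the SAP never specifies one.

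It is also fair to say that the size rests on figures the documents do not give, and that at 5% missing it is small. The simulations left out the MCMC step, the stratification covariates and bounded or ordinal scores. The MMRM on totals would help to expose an ANCOVA SE that is too small, but as a sensitivity analysis it cannot replace the gated p-value.

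**Conclusion.** The point holds conditionally. If the domains are imputed in separate runs, which is the more natural reading, the SE of the total-score ANCOVA is too small. At correlation 0.6 the shortfall for the 5-D, which is tested first, runs from about 2.5% at 5% missing to about 15% at 25% missing, with type I error from 5.8% to about 10%. For the Skindex-10 it is about 6% at 15% missing (7.1%) and 11% at 25% (8.2%). At correlation 0.3, five domains and 15% missing, it is about 6% (6.5%). The missing rate and the correlations are assumptions. If the domains are drawn jointly, the test is about nominal.

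Two stronger inferences are not supported. The treatment difference is not biased in this setting, because the total is a linear sum and dropout was at random; only its stated precision is wrong. The ≥4-point NRS test keeps its own level, since it uses the primary analysis's imputed data (SAP 8.2.4.3); it is affected only through easier passage of the gate.

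**What to change.** Before unblinding, state in SAP 8.2.4.3 that, for each questionnaire and within each arm, all domains at baseline and all visits, with the two stratification factors, enter one MCMC/monotone-regression model. The domains are drawn jointly, in one set of 20 imputations from which the totals are formed. Add sample code, as section 14 does for the NRS. If the joint model does not converge, impute the total score directly.

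The cost is SAP wording and a longer variable list in the same procedure. The downside is a larger model: 5 domains × 5 time points + 2 factors = 27 variables for the 5-D, and 3 × 5 + 2 = 17 for the Skindex-10, with 175 patients planned per arm. The fallback is there for that reason.
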